In LM+SHARE, counselors had access to a secure online portal that uploaded data from participants' self-monitoring devices. Counselors were instructed to attend to changes in weight, adherence to dietary intake and physical activity goals, and self-monitoring frequency when viewing data. In phone calls and text messages with participants, counselors used their data observations to cultivate a sense of supportive accountability, conveying to participants that they were regularly monitoring adherence to program goals in order to sustain participant success. Counselors set goals with participants in monthly phone calls, subsequently viewed data relevant to the goals to determine if they were being met, and in the text messages and phone calls that followed provided praise to reinforce positive behaviors or expressed concern if adherence was poor. For example, a text message might say: "I'm so impressed that you started recording your food intake again! I saw you recorded for 5 days this week. Reflect on how you accomplished that, and how it was helpful, so that you can carry this success forward. Keep up this fantastic work!" As another example, in a phone call a counselor might say: "You set a goal last month of 5 bouts of exercise per week, and I see that you only averaged 2 per week. Tell me more about what happened." Counselors also used phone calls and text messages to review core behavioral skills or strategies and encourage their use.

In the LM condition, counselors did not have access to device data. Counselors used participant self-report in monthly phone calls (prompted by questions such as, "How successful have you been in meeting your physical activity goals since our last call?") to assess progress and adherence. As in LM+SHARE, LM counselors reviewed one or more core behavioral skills or strategies in each phone call. All participants in the LM condition received standardized, weekly text messages that highlighted a core behavioral skill or strategy; messages in this condition were not personalized.

The seven counselors who provided treatment had degrees in psychology or a related field (1 = PhD, 4 = MA/MS, 2 = BA/BS). Counselors had previous training in behavioral weight loss and also completed a training workshop and weekly supervision for this study. All counselors provided both forms of treatment.

Measures

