Assessments were completed at weeks 0 (baseline), 13 (i.e., baseline of Phase II treatment), week 26, and week 52 (end of treatment).

Demographics. Age, gender, education, race, and ethnicity were self-reported at baseline.
Height and weight. At each assessment, research staff weighed participants using a Tanita
model WB-3000 digital scale. Participants were weighed in light street clothes without shoes.
Height was measured at baseline using a stadiometer. Measurements were taken twice and
averaged.

Physical Activity. Participants wore ActiGraph GT3X tri-axial, solid state accelerometers to measure MVPA at weeks 13 and 52. (To minimize "device burden," given that participants were asked upon enrollment to begin using three other self-monitoring devices, Actigraph measurements were not done at week 0.) Participants were told to wear the accelerometer for seven consecutive days during all waking hours, and data were considered valid when available for a minimum of four days for at least 10 hours per day. ActiLife software was used to calculate MVPA using established cut-points (16). Consistent with the intervention focus on bouted exercise, MVPA totals included only episodes of MVPA detected by the accelerometer to be \geq 10 minutes.

Self-monitoring engagement. Device data were collected on a secure online portal, which allowed for calculation of the percent of days during which weight was recorded on the Yunmai Smart Scale; \geq five foods were logged in the Fitbit app; and the Fitbit counted \geq 500 steps.

Treatment engagement. Engagement with treatment phone calls was calculated as the number of calls the participant completed during Phase II, out of 8 possible calls. The number of text messages sent by the counselor also was calculated.

Treatment satisfaction. Treatment satisfaction was measured using the Treatment Acceptability Questionnaire (17), with some items modified to reflect specific treatment components of the current study. This measure has good internal consistency and concurrent validity.

Perceived accountability. The "Perceptions of Accountability" subscale of the Supportive Accountability Scale (18) was administered to measure the extent to which the participants feel accountable to others to achieve their weight control goals. Reliability and validity for this scale has been established (18).

Data Analysis

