Retention was compared between the two conditions using Fisher's exact test. Permutation test was conducted to examine the difference between conditions in the number of phone calls and text messages (which could vary if a participant requested that contact be discontinued or temporarily suspended) and treatment acceptability ratings. Permutation test, a type of nonparametric test that uses sampling without replacement to test hypotheses, was chosen due to the violation of t-test assumptions in the data set (19). We conducted permutation based ANCOVA to compare self-monitoring engagement in Phase II between conditions controlling for Phase I self-monitoring engagement. This analytic method was implemented in the "permuco" package in R and has been shown to be robust to data with non-normal distribution (20). ANCOVA was used to test the difference in weight change between conditions, controlling for Phase I weight loss. Change in bouted MVPA during Phase II was compared between LM and LM+SHARE controlling for Fitbit-measured changes in Phase I MVPA using permutation based ANCOVA. One outlier for bouted MVPA at 13 weeks in the LM condition was removed from the analyses (MVPA was more than 3 SDs above others). Repeated measures ANCOVA was used to compare perceived accountability controlling for Phase I change. Analyses examined whether the effect of condition on weight loss during Phase II was mediated by change in monthly adherence to self-monitoring during the first 6 months of Phase II, or change in perceived accountability from weeks 13 to 26. If weight and MVPA outcome data were missing, the most recent data from the participant's digital scale or Fitbit, respectively, were used for imputation; if those data were not available, baseline data were carried forward. Strong associations were found between weight measured in clinic and via home digital scale (r= .995, p< .001 at 52 weeks), and between Actigraph and Fitbit measurements of MVPA (r = .60, p < .001 at 52 weeks), validating this missing data approach. The study was designed as a pilot randomized trial, with a focus on having a large enough sample for estimates of feasibility, acceptability, and effect sizes to be reliable. Data were analyzed in SPSS version 25 and R version 4.0.0.

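### For a missed clinic weight, the value entered depends on home-scale use, so the imputation rule can bias the self-monitoring mediation path and the arm comparison of weight change

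*Combined protocol and SAP*

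**What the plan says.** For missing weight and MVPA outcomes, the Data Analysis section says that "the most recent data from the participant's digital scale or Fitbit, respectively, were used for imputation"; then, "if those data were not available, baseline data were carried forward". It sets no limit on the age of the home reading and does not say which visit is meant by baseline. The Measures section applies that word both to week 0 and, for Phase II, to week 13.

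The same home scale feeds the self-monitoring measure. Under Measures (Self-monitoring engagement), the device portal "allowed for calculation of the percent of days during which weight was recorded on the Yunmai Smart Scale", alongside food logging and step counts.

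Under Phase II: Remote Maintenance Treatment, LM+SHARE counselors act on this behaviour: "Counselors were instructed to attend to changes in weight, adherence to dietary intake and physical activity goals, and self-monitoring frequency when viewing data". LM counselors see no device data.

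The effect of condition on Phase II weight loss is then examined as "mediated by change in monthly adherence to self-monitoring during the first 6 months of Phase II", with perceived accountability as a second mediator. The imputation approach is called validated because clinic and home weights correlated at r = .995 at week 52. The document gives no count of missing or imputed weights, by arm or overall, and no sensitivity analysis.

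**The concern.** Among participants who miss a clinic weight, regular home weighers receive a recent measurement. Those who stopped weighing receive an old reading or, with no home reading at all, a fixed earlier value. The poorest self-monitors are therefore the likeliest to have an outcome that is not a measurement near the visit. The b-path regresses weight change on adherence, so a rule that sets the outcome according to adherence can manufacture or hide the slope being estimated.

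The arm comparison is exposed in the same way. If LM+SHARE raises self-weighing as intended, fewer of its missing weights would be filled with old values than in LM. The pilot aims at reliable effect-size estimates, so a bias of either sign matters.

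The r = .995 does not settle this. It can only come from people with both a clinic and a home weight at week 52, and says nothing about those with an old reading or a carried-forward baseline.

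**Working it through.** The document states no sample size, missing-weight rate or effect size, so there is no figure to reproduce. Every number below except r = .995 and the visit weeks is an assumption.

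**Direction.** Let Y be the true change from week 13 (positive = regain), L the Phase I loss and M adherence. The outcome model is Y = β0 + c′·arm + b·M + γ·L + error. The rule replaces Y with Y*:
- week 13 carried forward: Y* = 0, a shift of -Y;
- week 0 carried forward: Y* = L, a shift of L - Y;
- old home reading capturing a fraction φ of the change: Y* = φY, a shift of -(1 - φ)Y.

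These shifts fall mostly at low M. With regain (Y > 0), the first and third pull low-M outcomes down and push b upward, masking a protective link. The second pushes b downward when L exceeds Y. With zero mean regain, the first and third have no average effect.

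**Size, large-sample simulation.** Inputs: M = 50 + 15·arm + N(0, 28), clipped to 0-100; Y = 3 + b(M - 57.5) + N(0, 5) kg; mean L 6 kg, SD 4; 20% of clinic weights missing, with probability proportional to exp(-M/25); home readings, when present, exact. Two versions of the fallback were used. In the frequent version a person has no usable home reading with probability 1 - M/40, floored at 0. In the restricted version this happens only when M = 0. Slopes are in kg per percentage point.

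| | Frequent fallback | Only if M = 0 |
|---|---|---|
| Given a constant | 7.8% (LM 11.2%, LM+SHARE 4.4%) | 2.3% |
| True b = 0, week 13 | +0.015 | about +0.006 |
| True b = 0, week 0 | -0.016 | about -0.006 |
| True b = -0.040, week 13 | -0.014 | -0.030 |
| True b = -0.040, week 0 | -0.045 | -0.041 |

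Week-13 loss is (0.040 - 0.014)/0.040 = 65% with the frequent fallback and (0.040 - 0.030)/0.040 = 25% with the restricted one. Week-0 inflation is at most (0.045 - 0.040)/0.040 = 12.5%. The asymmetry follows from the shifts. At M = 0 with b = -0.040, mean regain is 3 + 0.040 × 57.5 = 5.3 kg, so week 13 shifts the outcome by -5.3 kg and week 0 by only 6 - 5.3 = +0.7 kg.

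With the frequent fallback, a true arm difference of -0.55 kg becomes -0.20 (week 13) or -0.62 (week 0). At 5% missing, week 13 gives b = -0.033, about 17% lost. If low self-weighers instead receive old readings holding 0-30% of their true regain, b is -0.018.

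**Size, small-trial simulation.** 40 per arm; share of days weighed 0.45 (LM) and 0.65 (LM+SHARE), SD 0.3; L 6 kg, SD 3.5; SD of Y 5 kg; true b and true arm difference both 0; missingness either random or commoner in low self-weighers; 4,000 replicates. With no missing weights the test of b rejects in about 5%. At 30% missing:

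| Rule | Mean regain | Indirect effect a·b (kg) | Arm difference (kg) | Rejection |
|---|---|---|---|---|
| Week 0 | 0-4 kg | -0.10 to -0.67 | -0.09 to -0.65 | 6-40% |
| Week 13 | 0 kg | about 0 | about 0 | 4% |
| Week 13 | 2-4 kg | +0.10 to +0.45 | +0.13 to +0.46 | 5-24% |
| Old reading | 2-4 kg | +0.10 to +0.44 | +0.10 to +0.45 | 6-25% |

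At 5% missing, rejection stays between 4.5% and 6.2% in every scenario.

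**Does leaving the constants out cure it?** In the large-sample model it returns b = -0.040, but only because missingness there depends on M alone. When missingness also rises with regain (weight 1 per SD, 20% missing, frequent fallback), omission gives -0.026, week 0 about -0.034 and week 13 -0.009.

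**The case against.** The strongest reply is that the baseline fallback may hardly ever be reached. The rule takes the latest home reading whatever its age, and every participant was given a scale and told to weigh at home from week 1, so almost anyone who ever weighed at home has a reading. This stands, and it is why the restricted column above is closer to the literal rule than the frequent one. It does not remove the dependence: low self-weighers then tend to receive old readings, which act much like week-13 carry-forward.

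Second, the coupling is looser than simulated. Self-weighing is one of three components; the mediator is change in adherence over the first six months of Phase II, not its level; and perceived accountability is not directly tied to the rule. This also stands and dilutes the bias.

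Third, dropping the constants rests on a missing-at-random assumption that can fail, as the last calculation shows. That stands and shapes the remedy.

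A reader might go further and infer that the mediation link in this trial is partly an artefact, that the share given a constant does differ by arm, or that the choice of baseline visit alone fixes the direction. The document supports none of these. It gives no missing-weight counts, and the sign also depends on actual regain and on the age of the home reading. Nor can the problem be treated as separate from reading age, since under the literal rule an old reading is the likelier route.

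**Conclusion.** The concern holds as a possibility built into the rule. For missed clinic weights, the entered value depends on a behaviour that is part of the tested mediator and a target of LM+SHARE, so the self-monitoring b-path and the arm difference can both be biased. With regain, week 13 or an old reading tends to mask a link, and week 0 tends to create or inflate one. The quoted correlation does not bear on it.

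The size cannot be known from the document. Under the stated assumptions at 20% missing, the week-13 loss in b runs from about 25% to about 65%, depending on how often the fallback is reached. The week-0 change is small when a real effect exists, and everything shrinks towards nothing as missing weights become few. This is a cheap improvement to the analysis and gives no ground to discard the results.

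**What to change.** 1. In the self-monitoring mediation analysis, do not enter carried-forward baseline weights or home readings taken well before the visit. Use clinic weights or home readings within a stated window, and handle the rest by likelihood or multiple imputation conditioning on condition, Phase I weight loss and adherence.
2. Beside the carried-forward ANCOVA, report a likelihood or multiple-imputation analysis of the arm difference. Adherence should enter as an auxiliary variable for the missing data, not as a covariate in the arm model, where it would adjust away part of the effect of condition.
3. Name the baseline visit carried forward, and report by arm how many week-26 and week-52 weights came from clinic, home scale and baseline.
4. Keep the week-0 carried-forward result as a sensitivity analysis, because the missing-at-random assumption itself biases b if people who regain more are likelier to be missing.

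The cost is revised analysis wording and a re-run on existing data. The downside is fewer observed outcome values in the mediation model and reliance on missing at random.

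### A correlation of .60 at week 52 does not validate filling missing ActiGraph MVPA from Fitbit, and no conversion to the bouted ActiGraph scale is described

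*Combined protocol and SAP*

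**What the plan says.** Measures, Physical Activity, defines the outcome: "Participants wore ActiGraph GT3X tri-axial, solid state accelerometers to measure MVPA at weeks 13 and 52". On scoring, "MVPA totals included only episodes of MVPA detected by the accelerometer to be" at least 10 minutes long, and "data were considered valid when available for a minimum of four days for at least 10 hours per day".

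Data Analysis compares the Phase II change in bouted MVPA between arms, "controlling for Fitbit-measured changes in Phase I MVPA using permutation based ANCOVA". Where weight or MVPA is missing, "the most recent data from the participant's digital scale or Fitbit, respectively, were used for imputation", with baseline carried forward if no such data exist.

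The support offered is one sentence covering both outcomes. It opens "Strong associations were found between weight measured in clinic and via home digital scale (r= .995, p< .001 at 52 weeks") and continues with the relation "between Actigraph and Fitbit measurements of MVPA (r = .60, p < .001 at 52 weeks), validating this missing data approach". The same section describes the trial as a pilot, "with a focus on having a large enough sample for estimates of feasibility, acceptability, and effect sizes to be reliable".

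**The concern.** To stand in for a missing ActiGraph value, a Fitbit value must be on the same scale and centred in the same place. Correlation tests neither. The figure is given for week 52 only, although week 13 is also an ActiGraph visit that may need filling.

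The ActiGraph outcome has cut-points, a bout rule and a wear rule. For the Fitbit fill the documents give no bout rule, wear rule, time window or conversion. Direct substitution is the natural reading, but the mechanism is not stated.

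At stake is the arm contrast in MVPA change. If one visit is ActiGraph and the other Fitbit, any device difference is counted as Phase II change. Unequal fill between arms is plausible: LM+SHARE counselors watch self-monitoring frequency and respond to it, while LM counselors see no device data, so the availability or recency of Fitbit values could differ by arm. As the pilot aims at reliable effect sizes, a reader needs to know how far the MVPA effect rests on Fitbit values and whether the devices agree.

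**Working it through.** **The plan's figures.** From the documents: r = .60 (MVPA) and r = .995 (weight), both p < .001 at week 52. These are observed results and cannot be reproduced without participant data. The p-value can be put in context: t = r√((n−2)/(1−r²)). At r = .60 and n = 27, t = 0.60 × √(25/0.64) = 3.75 and p = .0009. So 27 pairs suffice for p < .001, and the test concerns r = 0, not agreement.

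**What r = .60 leaves open.** r² = .36, so the best linear prediction from Fitbit leaves a residual SD of √(1 − .36) = 0.80 ActiGraph SD. Assuming equal means and SDs, the 95% limits of agreement are ±1.96√(2(1−r)):
- MVPA: 1.96 × √0.80 = 1.96 × 0.894 = ±1.75 SD
- Weight: 1.96 × √0.010 = 1.96 × 0.100 = ±0.20 SD

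These are limits for one person. In a group contrast, random disagreement mainly adds noise. Adding a constant to every Fitbit value leaves r at .60, so r says nothing about an offset.

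**Route 1: offset with unequal fill.** Bias = d × (arm difference in net one-sided fill), where d is the Fitbit minus ActiGraph offset in SDs and net one-sided fill is the share filled at week 52 only minus the share filled at week 13 only. Assumed throughout: 40 per arm, unit SDs, ActiGraph week 13 to 52 correlation .6, Fitbit week 52 to ActiGraph week 13 correlation .36, week 52 only filled, at random, 20% in one arm and 30% in the other, no covariate adjustment.
- Change variance if observed: 2 − 2(.6) = 0.80. If filled: 2 − 2(.36) = 1.28.
- Arm variances at d = 0: 0.8(0.80) + 0.2(1.28) = 0.896 and 0.7(0.80) + 0.3(1.28) = 0.944, summing to 1.84. The offset adds (0.16 + 0.21)d² = 0.37d².
- SE = √((1.84 + 0.37d²)/40)

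| d (SD) | Size of bias (SD) | SE | Bias/SE |
|---|---|---|---|
| 0 | 0 | 0.214 | 0 |
| 0.25 | 0.025 | 0.216 | 0.12 |
| 0.50 | 0.050 | 0.220 | 0.23 |
| 0.75 | 0.075 | 0.226 | 0.33 |
| 1.00 | 0.100 | 0.235 | 0.43 |

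A simulation of permutation ANCOVA under no treatment effect (skewed outcome, same arm sizes and fill, 4000 replicates) gave false-positive rates of 4.8%, 6.0% and 7.7% at d = 0, 0.5 and 1.0. A second simulation on similar assumptions (3000 replicates) gave 4.6%, 5.1% and 6.7%.

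**Route 2: incomplete pickup of a treatment effect.** This needs neither an offset nor unequal fill. Assume 25% filled at week 52 in both arms, a true effect of 0.5 SD, and Fitbit following ActiGraph with slope 0.6. Filled participants then show 0.6 × 0.5 = 0.3 SD, and bias = 0.25 × (0.3 − 0.5) = −0.05 SD. If Fitbit registers the full effect, this bias is zero.

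**Cost of using ActiGraph data only.** SE = √(0.8(1/32 + 1/28)) = 0.231, against 0.214 for the current rule at d = 0. Mean squared errors are equal when 0.046 + 0.01925d² = 0.05357, that is d = 0.63. Below that offset the current rule does better, provided Fitbit registers the full effect.

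**How far the two estimates differ by chance.** With d = 0 and the same inputs, the variance of their difference is 0.2²(1.28/8 + 0.80/32) + 0.3²(1.28/12 + 0.80/28) = 0.0074 + 0.0122 = 0.0196, an SD of 0.14. In a simulation with normal outcomes, unadjusted t-tests, a true effect of 0.5 SD, full pickup and no offset, the two analyses fell on opposite sides of p = .05 in about 21% of trials.

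**The case against.** The best defence is that no harm is demonstrated. Arm sizes, fill rates, offset and slope are all assumed. Both arms were told to use their devices daily. Even the assumed biases are small, and the current rule beats ActiGraph-only analysis on mean squared error over much of the range. The Phase I activity goal was itself set in bouts of at least 10 minutes, participants were directed to the Fitbit's active-minutes measure, and a sample counselor call in the Phase II section refers to bouts of exercise seen in device data, so the Fitbit values may be on a similar scale. MVPA is not named as the primary outcome, and fill counts belong mainly in a results report.

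Most of this stands, and it limits the point to a correction and a check. It does not rescue the claim of validation. The references to bouts and active minutes are not tied to the fill rule and do not settle the scale.

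A reader might infer more: that raw Fitbit minutes were used, that the MVPA result is biased, or that the Fitbit rule should be dropped. The documents support none of these. The processing step is undescribed, no offset or arm-specific fill is reported, and dropping the Fitbit values loses precision. Nor would it be right to infer that bias vanishes whenever the offset is zero or fill is equal, since incomplete pickup operates even then. For weight, r = .995 and a shared unit make the same logical gap a much smaller concern.

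**Conclusion.** The point holds as a should-fix. The statement that r = .60 validates the fill is unsupported, and the step from Fitbit data to a bouted ActiGraph value is missing; confidence in both is high. The consequence is uncertain. Bias in the arm contrast is possible, not shown, and likely modest: at most 0.10 SD (0.43 standard errors) for offsets up to 1 SD with a 10-point difference in fill, and about 0.05 SD for incomplete pickup under the stated example. All of these sizes rest on assumed inputs. The current rule can stay as the main analysis once agreement and the amount of fill are visible.

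**What to change.** 1. In Data Analysis, remove the claim that the correlation validates the missing-data rule for MVPA, and report it as an association only.
2. State how Fitbit data become the filled value: substituted or converted, bouted or not, with what wear rule and what time window.
3. Report the paired Fitbit minus ActiGraph mean difference with 95% limits of agreement, and the number of MVPA values filled by arm, visit (13, 52) and source (Fitbit or carried forward). These cost least and tell most, because a bias near 0.05 SD is well inside the chance spread of 0.14 SD between the two analyses.
4. Keep the current rule as the main analysis and add a sensitivity analysis of the MVPA contrast on ActiGraph-observed data only. Compare estimates and intervals, not whether each crosses p = .05. If the estimates differ materially, describe the MVPA effect as dependent on the fill method.
5. Optionally, if enough participants have both devices, calibrate Fitbit to ActiGraph bouted MVPA by regression with arm in the model. In simulation with a true effect of 0.5 SD, leaving arm out biased the estimate by about −0.07 SD. The number with both devices is not given, so the calibration may be imprecise.

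The cost is a text correction and a little more analysis on data already held, since follow-up ended in May 2019. The ActiGraph-only interval will be somewhat wider (SE about 0.231 against 0.214 SD under the assumed inputs).
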